5 STUDY EVALUATIONS AND MEASUREMENTS

5.1 Screening and Monitoring Evaluations and Measurements

5.1.1 Medical Record Review

Include a listing of the variables that will be abstracted from the medical chart (paper or electronic).

- Date of birth
- Date of diagnosis and treatment history
- Medications
- Length of hospitalization prior to starting the study
- Number of visits completed or declined with supportive services (physical therapy, occupational therapy, school, creative arts therapies, and/or psychology) for each study period (Days 0-+4 including nights, Days +5-+9 including nights, Days +10-+14 including nights).
- Frequency and timing of vitals checks for each day in the study.
- Medications used for supportive care for each study period (Days 0-+4 including nights, Days +5-+9 including nights, Days +10-+14).
- Transplant parameters including: type of transplant, disease status, cell processing, GVHD prophylaxis and infectionus prophylaxis.

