3 INVESTIGATIONAL PLAN

3.1 General Schema of Study Design

Patients undergoing HSCT face many challenges to restful sleep during the hospitalization for transplant. Frequent vitals checks, necessary during conditioning and immediately post-transplant, may be less necessary as time from transplant increases. Utilizing an aggregated N=1 randomized trial design (Figure 1. Study Flow), the current study will test protecting one 6-hour window for sleep within patients recovering from HSCT. This study will assess the acceptability and feasibility of this intervention, evaluate the impact on patient sleep, and test how sleep is related to symptom burden, engagement in supportive services, and HRQL during HSCT recovery. Participants will wear an actigraph for the duration of the study (day of the transplant [day 0] through the night of Day +14post-transplant, removing the actigraph upon awakening on Day +15) to measure sleep accompanied by a brief sleep diary sent daily by text messages delivered via REDCap and its integration with Twilio.

Participants will complete self-report measures of sleep, symptom burden, and HSCT related

HRQL at baseline and at the end of each study period (Day +5, +10, +15; Table 1 Study Procedures).

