3.1.2 Study Treatment Phase (start of the study intervention)

One-two days before the transplant, a study team member will meet with the family to complete the informed consent, baseline measures, and give actigraphy instructions. All patients will wear an actigraph from the day of the transplant until day +5 from the transplant to serve as the “observation baseline” for each patient.

3.1.3 Phase 2

On Day +5, to reduce the impact of expectancies during the first observation period, patients will be randomized to ABA (observation/intervention/observation) or AAB (observation/observation/intervention), with each period lasting 5 days (Fig. 1). Block randomization stratified by age will be used to ensure similar age distribution between groups. The two group design will allow for the comparison of altering vitals checks before/after engraftment and peak symptom burden (typically on day +10⁴). On each intervention night, the research team will verify with the child's provider that it is acceptable for the patient to have a 6-hour window between vitals checks. This confirmation will be communicated to the child's nighttime nurse. For the 5 days of the child's intervention period, the nurse will be instructed to conduct the last vitals check between 9pm-1am. After the last vitals check, the patient will be given 6 hours until the next vitals check, unless the caregiver/patient request nursing. Patients will continue to wear the actigraph until the end of the study. The patient can remove the actigraph upon awakening on Day +15.

Eligibility for extended vitals check, assessed daily: 1) No fever in the last 24 hours; 2) No concurrent chemotherapy administration; 3) No ongoing or active infection; and 4) No organ toxicity requiring labs more than every 6 hours. Even if a patient is ineligible for extended vitals checks they are asked to continue to wear the actigraph.

After each patient has completed both the intervention and a second observation (either BA or AB), they will be asked to complete final study measures and measures of acceptability of the intervention.

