3.2 Allocation to Treatment Groups and Blinding

Participants will be randomized to either Observation/Intervention or Intervention/Observation on day +5 post-transplant. The research coordinator will generate a randomization sequence using a random number generator, with block randomization occurring based on participant age (8-12 or 13-21). Blinding will not be possible, but randomization will occur on day +5 to minimize the impact of the intervention on the initial observation period.

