5.1.2 Other Evaluations, Measures

Subjects and caregivers will complete the following measures:

| Table 1. Study Measures. | | Baseline | Day +5 | Day +10 | Day +15 |
|--------------------------|--|----------|--------|---------|---------|
| Construct | Measure | | | | |
| Acceptability | Patient, caregiver, and nurse will respond to a brief questionnaire of acceptability of adjusting vitals checks. | | | | x |
| Demographics | Report of sex, race/ethnicity, age of child and caregiver | x | | | |
| COVID-19 Impact | COVID-19 Exposure and Family Impact Survey (CEFIS) to assess family exposure to and experience with COVID-19 through Yes/No responses (25 items); 12 items assessing the impact of the pandemic on | x | | | |

| | | | | | |
|---------------------------|---|---|---|---|---|
| | self/family with 1-4 intensity scale and 1 open-ended item | | | | |
| HRQL and related symptoms | Pediatric Quality of Life Inventory—Stem Cell Transplant Module. This measure assesses HRQL and symptoms relevant to patients undergoing HSCT. The measure includes questions about pain, fatigue/sleep, nausea, communication, worry, nutrition, thinking and other symptoms answered on parallel child and adolescent with parent proxy forms (41 items). ²⁶ | x | x | x | x |
| Sleep | PROMIS Sleep Measures—Sleep disturbance, sleep-related impairment, and sleep hygiene over the past week-parallel parent/child forms (24 items) ²⁷ . | x | x | x | x |
| Supportive Care Use | EHR review to document engagement or refusal of PT/OT/School/Creative Art Therapy/ Psychology for each 5 day period. | | x | x | x |
| Actigraphy | Worn by participant day 0-night of Day +14, removing on awakening on Day+15. To validate actigraphy: bedtime, waketime, night awakenings, naps, time actigraph was off reported daily through text messages delivered via REDCap and its integration with Twilio. | | | | |

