6.3.2 Efficacy Analysis

Using descriptive statistics, feasibility will be determined by assessing medical eligibility for the intervention and the delivery of the intervention. Descriptive statistics will be used to characterize acceptability measure responses

Secondary endpoints will include the change in sleep parameters and engagement in supportive care services. We will utilize hierarchical multilevel mixed-effects models for daily diary data, which uses all available data, allows for multilevel nesting (e.g., daily data nested within participants, nested within condition), and are fairly robust to missing data (models are valid under Missing At Random assumption)²⁸. Fixed and random effects models will be fit to the data²⁹ to estimate the impact of the intervention on nocturnal sleep (sleep efficiency, total sleep time, night awakenings); Aim 2) and engagement in supportive care, HRQL, and symptom burden (Aim 3). We will test for carryover effects of the intervention and adjust analyses as needed²⁹.

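### Supportive-care visits are kept only as 5-day totals, so engagement cannot be matched to the preceding night, and uneven weekday counts add avoidable noise

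*Combined protocol and SAP*

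**What the plan says.** Section 5.1.1 lists, among the items taken from the chart, the "Number of visits completed or declined with supportive services", one figure per study period (Days 0 to +4, +5 to +9, +10 to +14). The measures table in 5.1.2 agrees: "EHR review to document engagement or refusal of PT/OT/School/Creative Art Therapy/ Psychology for each 5 day period". The same list in 5.1.1 takes a different approach to vitals: "Frequency and timing of vitals checks for each day in the study". Actigraphy is worn every night.

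The abstract and the nurse consent plan (9.6) place the intervention on the nights of Days +5 to +9 or +10 to +14. Section 9.4.3 expects any benefit to show in functioning on the day after. Section 3.1.3 assesses eligibility for the longer interval daily, so a child may have fewer than five protected nights. On order, 3.2 states: "Participants will be randomized to either Observation/Intervention or Intervention/Observation on day +5 post-transplant".

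The engagement endpoint (6.2) is the change between observation and intervention periods. It is not said whether this is a count of visits or a share of visits offered. Section 6.3.2 begins "We will utilize hierarchical multilevel mixed-effects models for daily diary data" and later names engagement, with HRQL and symptom burden, among the outcomes to be modelled. It gives no level of analysis, distribution or calendar term for engagement. Section 3.1 also promises to "test how sleep is related to symptom burden, engagement in supportive services, and HRQL during HSCT recovery".

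**The concern.** The intervention acts at night and supportive care is presumably delivered by day. A period running from Day +5 to Day +9 contains the daytime before its first night and leaves out the daytime after its last. If better sleep raises engagement the next day, as the protocol supposes, some days are counted under the wrong condition and the estimated effect shrinks towards zero. A 5-day total cannot be re-cut to correct this, nor can it be linked to the nights on which the window was actually protected.

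The second issue is the calendar. Five consecutive days hold 3, 4 or 5 weekdays. If therapists and teachers work mainly on weekdays, the number of visits a child can be offered changes between that child's own periods for reasons unrelated to sleep. The pilot is meant to supply effect sizes for a future trial (6.4), so a diluted or noisier engagement estimate would be carried forward.

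**Working it through.** The plan gives no calculation for this endpoint, so there is no stated figure to reproduce.

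**1. Alignment with the preceding night**

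Inputs: intervention nights +5 to +9 (ABA) or +10 to +14 (AAB); totals over Days +5 to +9 (period 2) and +10 to +14 (period 3). Assumptions: each protected night changes engagement only on the following day, by the same amount, with equal opportunity each day.

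- ABA: affected days are +6 to +10. Period 2 holds 4 of 5 affected days and period 3 holds 1 of 5 (Day +10). Contrast = 4/5 − 1/5 = 3/5, or 60% of the daily effect.
- AAB: affected days are +11 to +15. Period 3 holds 4 of 5 and period 2 holds none. Contrast = 4/5 − 0 = 80%.
- Average with 1:1 allocation (ratio not stated): (60% + 80%)/2 = 70%.

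If the effect is spread over several days, or partly same-day, these fractions change.

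**2. Weekdays per period**

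Count of Monday-to-Friday days by weekday of Day 0:

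| Day 0 | Days 0 to +4 | Days +5 to +9 | Days +10 to +14 | Period 2 − period 3 |
|---|---|---|---|---|
| Mon | 5 | 3 | 3 | 0 |
| Tue | 4 | 4 | 3 | 1 |
| Wed | 3 | 5 | 3 | 2 |
| Thu | 3 | 4 | 4 | 0 |
| Fri | 3 | 3 | 5 | −2 |
| Sat | 3 | 3 | 4 | −1 |
| Sun | 4 | 3 | 3 | 0 |

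Periods 2 and 3 differ for 4 of 7 start days, by at most 2 weekdays. The documents do not say which days services run. If weekend service is a fraction w of the weekday level, a 3-weekday period offers (3 + 2w)/5 of a 5-weekday period: 60% for w = 0, 80% for w = 0.5 and 100% for w = 1.

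**3. Bias or noise?**

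For any Day 0, intervention minus observation weekdays is +d under one order and −d under the other, so the expected imbalance between periods 2 and 3 is 0. With start days equally likely, the SD per child is √[(0+1+4+0+4+1+0)/7] = √(10/7) = 1.20 weekdays. The chance imbalance in the mean then has SE 1.20/√16 = 0.30 weekdays for the 16 subjects in 6.4, or 1.20/√50 = 0.17 for the 50 evaluable in 3.3.2. (Those two sample sizes differ; this point does not depend on which applies.)

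Period totals were simulated 2,000 times: Poisson counts, one visit per weekday on average, weekday-only service, 1:1 order. Periods 2 and 3 were compared within child with a period effect, without and with a log(weekdays) offset. Estimates are log rate ratios, and SEs are empirical.

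| N | True value | Estimate (SE), no offset | Estimate (SE), offset | SE ratio |
|---|---|---|---|---|
| 16 | 0 | −0.005 (0.224) | −0.003 (0.209) | 1.07 |
| 16 | 0.182 | 0.187 (0.214) | 0.186 (0.195) | 1.10 |
| 50 | 0 | −0.006 (0.122) | −0.005 (0.112) | 1.09 |
| 50 | 0.182 | 0.182 (0.118) | 0.182 (0.108) | 1.09 |

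The unadjusted estimate is essentially unbiased, with an SE 7 to 10% larger. The simulation covers the calendar issue only, not the misalignment in step 1.

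**4. Pooling period 1**

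Period 1 is always observation, so randomized order does not balance it. If all transplants fell on a Monday (5/3/3), intervention would have 3 weekdays against an observation mean of (5 + 3)/2 = 4 in either sequence. With Monday to Friday equally likely, the means are 3.70 and 3.65. Transplant weekdays are not given, and the gap would matter only if period 1 is pooled without a period or weekday term.

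**The case against.** The formal objective (2.2) and endpoint (6.2) compare engagement between periods, which is the level at which it is abstracted. Section 6.3.2 attaches the daily model to diary data and lists engagement beside HRQL, which is measured once per period. A period-level mixed model is therefore a fair reading, and the sleep-engagement aim in 3.1 names no next-day lag. This stands: the documents do not commit to a daily model of engagement that the data would be unable to feed.

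A reader might infer that calendar differences cannot be separated from the intervention effect. The documents do not support that. Weekdays per period follow from the Day 0 date, which the site must know to run the visits, so they can enter a period-level model as an offset. Randomized order keeps the imbalance between periods 2 and 3 from being systematic. Declined visits are also abstracted, so completed/(completed + declined) can be computed from the planned totals and would partly correct for fewer offers.

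A reader might also count 15 dated observations per child against 3 as a fivefold gain. Days within a child are correlated, and without weekend service only 10 or 11 service days remain (Sat 3+3+4 = 10; Mon 5+3+3 = 11).

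Finally, 6.3.2 plans a carryover test. It might pick up the Day +10 spillover in ABA, but it does not address Day +5, and from totals a one-day lag cannot be told from a longer carryover. Neither an offset nor a share restores the link to the preceding night.

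**Conclusion.** The point holds as a low-cost improvement to a secondary endpoint of a pilot. It is not a flaw that invalidates the analysis. The main loss is alignment: under a purely next-day, additive effect, the period 2 v 3 contrast recovers 60% (ABA) or 80% (AAB) of the daily effect, and totals give no means of correcting it or of relating engagement to nights actually protected. The calendar loss is smaller and conditional: about 7 to 10% on the standard error if services run only on weekdays, less if weekend service is reduced but present, and nothing if it is equal. It can be removed without daily abstraction. Systematic calendar bias would need transplants clustered on particular weekdays together with unadjusted pooling of period 1, and the documents establish neither.

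**What to change.** In 5.1.1, abstract each supportive-care visit with its service, calendar date and status (completed or declined), and make the same change in the 5.1.2 table.

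In 6.3.2:

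- Define engagement, for example completed/(completed + declined), and state its level of analysis.
- Classify each day by whether the preceding night was a scheduled intervention night. An analysis by nights actually protected can be added as supplementary. It should be read with care, because nights lost to fever or infection are also likely to be days of low engagement.
- Fit a mixed model with condition, study day and weekday/weekend, and a random intercept for child. If services do not run at weekends, keep service days only; in a period-level model the equivalent is a log(weekdays) offset.
- Report period totals of completed and declined visits alongside, since a share hides how many visits were offered.

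Under this classification ABA has five days following an intervention night (+6 to +10) and AAB four (+11 to +14), unless abstraction is extended to Day +15.

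The cost is slightly more data entry in the same record review. Totals can be rebuilt from dates, whereas dates cannot be recovered from totals without repeating the abstraction.

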| HSCT | Hematopoietic stem cell transplant |
| HRQL | Health-related quality of life |
| AE | Adverse event |
| EHR | Electronic Health Record |
| MRN | Medical Record Number |

ABSTRACT

Context: Patients undergoing treatment for cancer face disease, treatment, and environmental obstacles to sufficient, sound sleep¹. Hospitalizations can further worsen sleep quality and quantity due to overnight vitals checks, medication administration, blood draws, and environmental noise and light². For patients undergoing hematopoietic stem cell transplant (HSCT), the risk for poor sleep is especially high due to protracted hospitalization, frequent vitals checks resulting in multiple night awakenings³, and high symptom burden peaking approximately 10 days post-transplant⁴.

Objectives:

Primary: Test the acceptability and feasibility of protecting one 6-hour window for nighttime sleep (intervention) relative to regular vitals checks (observation only periods) during HSCT recovery.

Secondary: Assess the effect of one 6-hour window for nighttime sleep on subject sleep and engagement in supportive care on the HSCT unit.

Study Design:

Aggregated N=1 randomized controlled design. All participants will undergo a 5 day observation and then be randomized to receive the 5 day intervention (extended vitals checks) during either nights of days +5-+9 or days +10-+14.

Setting/Participants:

Inpatients on the HSCT Unit at CHOP

Study Interventions and Measures:

[figure not shown]
Intervention—increasing time between vitals checks from every 4 hours to one 6-hour period at night.

Subjects will wear an actigraph for the duration of the study, complete a daily sleep diary, and complete self- and parent-proxy psychosocial measures (symptom burden, health related quality of life, sleep) and acceptability. Medical record review will also be conducted to assess vitals check frequency.

TABLE 1: SCHEDULE OF STUDY PROCEDURES

| Visit | Purpose | Main Procedures | Duration |
|--------------------------------|--------------------------|--|------------|
| Visit 1 Pre-transplant | Baseline measures | Complete Informed consent Complete CEFIS Complete self-report measures Give actigraph | 35 minutes |
| Visit 2, Transplant Day 0 | Start actigraph | Review actigraphy procedures | 5 minutes |
| Visit 3, Transplant Day +5 | Randomization | Randomize to intervention start Complete self-report measures | 20 minutes |

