| Visit 4, Transplant Day +10 | Psychosocial measures | Complete self-report measures | 15 minutes |
| Visit 5, Transplant Day +15 | End of Study | Return actigraph, Complete self-report measures including acceptability measure | 20 minutes |

.

FIGURE 1: STUDY DIAGRAM

*Each study period will include nights and symptom burden and sleep will be collected the day following the end of the study period. For example, sleep from night +4 and symptom burden for the day 0-+4 period will be collected on day +5.

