1 BACKGROUND INFORMATION AND RATIONALE

1.1 Introduction

Patients undergoing treatment for cancer face disease, treatment, and environmental obstacles to sufficient, sound sleep¹. Hospitalizations can further worsen sleep quality and quantity due to overnight vitals checks, medication administration, blood draws, and environmental noise and light². For patients undergoing HSCT, the risk of poor sleep is especially high due to protracted hospitalization, frequent vitals checks resulting in multiple night awakenings³, and high symptom burden peaking approximately 10 days post-transplant⁴. Sleep quality and quantity is associated with immune functioning⁵, wound healing⁶, and resistance to infection⁷, all critical to physical recovery from cancer and cancer treatments. Poor sleep may also have a psychosocial impact by limiting engagement in supportive care (PT/OT/School/Creative Arts Therapy/Psychology) due to compensatory daytime sleep and fatigue⁸. Together the physical impact of poor sleep and limited engagement in supportive care may hinder HSCT recovery. Frequent vitals checks are one potential intervention target when seeking to improve sleep. Vitals checks every 4 hours are necessary during conditioning and immediately post-transplant, but for many patients extending the time between vitals checks is possible. Through an aggregated N=1 randomized controlled design (each patient will serve as their own control, with the timing of the 5-day intervention period determined by randomization), the current study will test acceptability, feasibility, and impact on sleep and supportive care engagement of protecting one 6-hour window for nighttime sleep (intervention) relative to regular vitals checks (observation) during HSCT recovery.

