6.2 Secondary Endpoints

Secondary endpoints will include the following:

- The change in sleep between observation and intervention period as measured by actigraphy sleep efficiency, total sleep time, and number of awakenings.
- The change in engagement in supportive services between observation and intervention period (physical therapy, occupational therapy, school and/or psychology) as measured through EHR review.

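### Supportive-care visits are counted in day blocks that open before the first protected night, so a next-day effect on this secondary endpoint would be diluted by about 20–30%

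*Combined protocol and SAP*

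**What the plan says.** Section 6.2 lists supportive-care engagement as a secondary endpoint: "The change in engagement in supportive services between observation and intervention period". Section 5.1.1 counts visits completed or declined over "Days 0-+4 including nights, Days +5-+9 including nights, Days +10-+14 including nights". The measures table in 5.1.2 says only "Psychology for each 5 day period", without giving the day ranges.

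The Abstract places the intervention "during either nights of days +5-+9 or days +10-+14", and the nurse consent plan in 9.6 gives the same nights. Section 3.1.3 fixes the clock time: "the nurse will be instructed to conduct the last vitals check between 9pm-1am", with the six protected hours after it. Night N follows day N: the note to Figure 1 has night +4 reported on Day +5, and Section 3.1 has the actigraph removed on waking on Day +15, after night +14.

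The rationale runs from night to day. Section 1.1 describes poor sleep as "limiting engagement in supportive care (PT/OT/School/Creative Arts Therapy/Psychology) due to compensatory daytime sleep and fatigue", and Section 9.4.3 places any gain in functioning on the day after. Section 6.3.2 plans mixed models and a test for carryover, with adjustment if needed.

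**The concern.** The visit blocks and the protected nights carry the same day numbers, but services take place in the daytime and protection starts that evening. A block labelled intervention therefore opens with a daytime that no protected night has preceded. On Day +5 part of that daytime may even precede allocation: "Participants will be randomized to either Observation/Intervention or Intervention/Observation on day +5 post-transplant". At the other end, the daytime after the last protected night is counted as observation in ABA (Day +10) and not counted at all in AAB (Day +15).

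No visible text gives visits an offset. The Figure 1 note, "Each study period will include nights and symptom burden and sleep will be collected the day following the end of the study period", concerns sleep and symptom burden only. Section 6.4 says the pilot is meant to supply effect sizes for a future trial. An effect size biased towards zero would be carried into that planning, and more participants would not remove the bias.

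**Working it through.** **Inputs.** Blocks of 5 days: 0–4, 5–9, 10–14 (5.1.1). Protected nights: 5–9 in ABA, 10–14 in AAB (Abstract, 9.6). Night N follows day N (Figure 1 note, 3.1). The plan states a period length of 5 days (3.1.3), and both the day blocks and the runs of nights contain 5.

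**Step 1: exposed daytimes.** Call daytime d exposed if night d−1 was protected.

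| Sequence | Block 1 | Block 2 | Block 3 |
|---|---|---|---|
| ABA | 0/5 | 4/5 (Days 6–9) | 1/5 (Day 10) |
| AAB | 0/5 | 0/5 | 4/5 (Days 11–14) |

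**Step 2: share of a next-day effect recovered.** Set the true effect to 1, with all nights delivered, equal service availability every day and equal sequence sizes. Least squares on the six sequence-by-block means, with sequence effects, reduces to:

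- No period or carryover term, intervention minus the mean of the observation blocks: ABA 0.8 − (0 + 0.2)/2 = 0.70; AAB 0.8 − 0 = 0.80; average **0.75**.
- Period effects, block 2 against block 3: ABA 0.8 − 0.2 = 0.60; AAB 0.8 − 0 = 0.80; average **0.70**.
- Carryover term, with or without period effects: it absorbs ABA block 3, leaving **0.80**.

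**Step 3: leave out the transition daytimes.** Use Days 0–4, 6–9 and 11–14. Exposure becomes ABA 0, 1, 0 and AAB 0, 0, 1, so all four models recover 1.00. They also recover 1.00 if engagement changes on the block's own dates, or from the block's first daytime through the day after its last protected night.

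**Step 4: precision.** With independent days, a 4-day mean has 5/4 = 1.25 times the variance of a 5-day mean. In units of the SD of a 5-day mean, with n/2 participants per sequence, the contrast has these SEs, each multiplied by 1/√(n/2):

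| Model | Planned | Transition days out | Ratio |
|---|---|---|---|
| Neither term | √0.75 = 0.866 | √0.906 = 0.952 | 1.10 |
| Carryover | 0.926 | 1.003 | 1.08 |
| Period | √1.00 = 1.000 | √1.25 = 1.118 | 1.12 |
| Both | √4.00 = 2.000 | √4.50 = 2.121 | 1.06 |

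At a within-period correlation of 0.2 the ratios fall to 1.03–1.05. Effect over SE, relative to full recovery at the planned SE, is 1/1.118 = 0.89 to 1/1.061 = 0.94, against 0.70–0.80 as planned.

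**Step 5: scale.** For an assumed true effect of 0.5 SD of a period mean, the loss is 0.20 × 0.5 = 0.10 to 0.30 × 0.5 = 0.15 SD. With period effects (0.15 SD lost), the SE is 1/√8 = 0.35 at 16 participants (6.4) and 1/√25 = 0.20 at 50 (3.3.2). With both terms (0.10 SD lost), it is 0.71 and 0.40.

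**Step 6: other effect shapes (assumptions).**

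- A second day at half strength, scaled to a steady state of 1. Planned blocks (ABA 0, 0.733, 0.267; AAB 0, 0, 0.733) recover 0.60–0.73. With transition days out (ABA 0, 0.917, 0.083; AAB 0, 0, 0.917), recovery is 0.88–0.92.
- Slow build-up, proportional to protected nights among the last five. Planned blocks (ABA 0, 0.4, 0.6; AAB 0, 0, 0.4) recover 0.10–0.40. With transition days out (ABA 0, 0.5, 0.5; AAB 0, 0, 0.5), recovery is 0.25–0.50. Neither is adequate.

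**The case against.** **Effect shape.** Section 9.4.3 speaks of functioning, not visits, and Section 1.1 names a mechanism without a lag. Section 1.3 expects a broader benefit over recovery. This stands: 20–30% is conditional on a next-day effect. A reader might infer that 2 of 15 daytimes in ABA and 1 of 15 in AAB are simply mislabelled, but that holds only under that effect shape.

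**Expectancy.** Care is unblinded, and Section 3.1.3 places randomisation on Day +5 to keep expectancy out of the first observation period. Moving every window one day later, to Days +1–+5, +6–+10 and +11–+14, would put the randomisation day inside that period. If engagement shifted from the block's first daytime, those windows would recover only 0.77–0.80 (0.40 with period and carryover terms), against 1.00 as planned. This stands in full and rules out a simple shift as the main analysis.

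**Carryover.** Section 6.3.2 already provides a test and adjustment. This stands in part. The adjustment can absorb Day +10 in ABA, but it cannot restore the unexposed first day of either intervention block, and AAB has no later block. Combined with period effects, it also doubles the SE (1.0 to 2.0).

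**Importance.** The primary endpoint is descriptive feasibility and acceptability, and the loss in the 0.5 SD example is below one SE. This stands. A reader might infer that the trial needs 1/0.75² = 1.78 to 1/0.70² = 2.04 times its sample. The documents do not support that: Section 6.4 claims no power for this endpoint.

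**Visibility.** Figure 1 is not shown, so a boundary drawn there could not be checked.

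**Conclusion.** The misalignment is in the protocol's own day and night definitions and needs no outside figure. Under a next-day effect, full delivery and equal daily service availability, the planned contrast recovers 0.70–0.80 of the effect; carryover adjustment brings it to 0.80 at best. If engagement moved with the block's own dates, the planned blocks would lose nothing. If the effect built up slowly, none of the windows considered would capture it well.

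It would be wrong to extend this to the primary endpoint or to the actigraphy sleep measures, whose nights coincide with the protected nights. It is a modest point about one secondary endpoint in a pilot. It is worth correcting because the bias is systematic, the pilot is meant to supply effect sizes, and the remedy is cheap.

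**What to change.** In Section 5.1.1, and in the supportive-care row of the 5.1.2 table, replace the per-period count with a rule such as this:

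*Visits completed or declined will be abstracted by calendar date. The endpoint is visits per day over Days 0–+4, +6–+9 and +11–+14; the transition daytimes, Day +5 and Day +10, are left out in both sequences. Two sensitivity analyses will be reported: counts over the full 5-day blocks, and an analysis attributing each daytime to the condition of the preceding night.*

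This keeps the randomisation day out of the first observation window, needs no Day +15 data and adds no participant procedure. Dated visits could also enter the daily-level models of Section 6.3.2, which the plan introduces for diary data.

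The cost is adding dates to visits already taken from the EHR, one coding rule, and two of 15 daytimes. The SE of the contrast rises by about 6–12% if days are independent, and by less if they are correlated. If services are not offered equally on every day, these figures change; the documents give no visit schedule.
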